4.3 Study Enrollment Procedures

Recruitment and Screening

For all phases, participants will be recruited from the community and through outpatient primary care and specialty mental health clinics. We will recruit from the community using social media, schools, and flyers in local businesses that cater to adolescents. We may include advertisements on city buses that take teens to school. We will recruit on Facebook, Instagram, Craig's List, and other social media sites if needed. We will post study information on a study website hosted by Butler Hospital; social media ads and posters will direct participants to the Butler website, where participants can request contact from the study staff. When an adolescent (or parent) calls or indicates interest, a research assistant will describe the study to the adolescent and parent by telephone. If they are both interested in having the adolescent participate, the RA will assess some inclusion criteria by phone (i.e., a phone screen).

For Phase 1, the RA will assess all inclusion criteria by phone once they have verbal agreement from the adolescent and the parent. RAs will tell the adolescent and parent what types of questions will be asked as part of the screening process, and then document that both the adolescent and parent have agreed to being screened by phone prior to beginning the actual screening process. The phone screen will be used to determine eligibility; there will be no other eligibility determination. The RA will administer the PHQ-8, will inquire about age, engagement in yoga, ability to attend a focus group, and medical clearance. If the adolescent is eligible, the RA will schedule the adolescent and parent to attend focus groups that will occur within the next 30 days.

For Phase 2, Phase 3 Study A, and Phase 3 Study B, the RA will describe study procedures to the adolescent, including what questions will be asked as part of the screening process on the phone. The adolescent will be made aware that the written consent of the adolescent's parent is needed to proceed in the study itself, if the adolescent is 17 years old or younger. RAs will seek verbal agreement from the adolescent and document that agreement occurred prior to beginning the actual screening process. RAs will then assess the following inclusion criteria by phone after obtaining verbal agreement from the adolescent:

- a) Adolescents must be able to read and write English sufficient to complete informed consent and engage in interventions.
- b) Adolescents must be aged 13-18.
- c) Able to attend one of the class times.
- d) Adolescents cannot currently be engaged in yoga classes.
- e) Other depression treatment is stable
- f) Access to a private space in their home for study classes, and a device that will support use of the video platform we are using to conduct assessments and classes.

In addition, by phone, the RA will verify that:

- a) The adolescent is currently experiencing some degree of depression symptoms (i.e., PHQ-8 ≥ 8).
- b) They are able to participate in physical activity, and either have a form signed by their pediatrician or are able to get one.

If adolescents appear potentially eligible by phone, the RA will:

- a) Conduct a verbal consent (with parent if teen is 17 or younger) to send an email link and conduct a Zoom video meeting;
- b) Schedule that meeting to obtain informed consent by parent (if aged 17 or younger) and assent from adolescent, or informed consent from 18 year old participant.
- c) Email links to the Zoom meeting, electronic informed consent, and electronic assent for teen

Informed Consent Procedures

Research assistants will perform this process. An electronic-signed consent form will be obtained from each participant using procedures outlined by the Butler Hospital IRB. Via video call and review of an electronic version of consent/ assent forms, all participants and parents will be fully informed of the purposes and procedures of the study. On the consent form and orally, participants will be given information about: who is sponsoring the study; a description of study procedures, including the process of randomization and the nature of the assessments; risks and inconveniences; benefits; compensation for study participation; alternative treatment options;

confidentiality, including the limits to confidentiality; the voluntary nature of their participation; and who to contact should they have questions. After making sure that the participant and parent have a full understanding of the nature and purposes of the study, the research assistant will obtain assent (consent if 18) from the adolescent and informed consent from the parent. For adolescents aged 17 and under, the parent will e-sign two consent forms: one for the adolescent to participate (required), and one for the parent to participate in assessments themselves (not required for the adolescent to participate). Adolescents aged 18 may also choose to have their parents participate by completing assessments, but it is not required. Assent/consent will be documented through the individual's e-signature on the respective forms, which will be kept in the CNE instance of REDCap. Participants and parents will be invited to print a copy of the assent/consent form to keep.

In Phase 1, we will begin the focus group immediately after conducting informed consent.

In Phase 2 and Phase 3, at the BL video-based visit, we will confirm inclusion criteria previously assessed via phone screen and assess the remainder of the inclusion criteria. Parents or adolescents aged 18 will next be asked to sign a release of information form that will allow us to contact their pediatrician by fax, describe the study, and request medical clearance to participate in mild-moderate physical activity. As an alternative, we will accept a form from their pediatrician in the prior year that states the adolescent may participate in school or camp programs including physical education. If the adolescent has a mental health provider, we will ask for a release of information to contact their MH provider to provide information about the study. Doing so establishes a relationship should we need to contact them in the future due to significant clinical deterioration or the development of active suicide ideation. Adolescents cannot begin classes until we gain medical clearance.

Enrollment and Randomization

In Phase 1, participants are considered enrolled immediately after signing the consent form.

In Phase 2, once we have medical clearance to participate in physical activity from a participant, and talk with the participant to confirm their interest, they are considered "enrolled." Enrollment may occur at the BL visit or at a separate BL2 phone call (if there is a need to request and wait for medical clearance). BL2 must occur within 14 days of BL1.

In Phase 2, adolescents are invited to attend classes within a week after enrollment.

Randomization occurs in Phase 3 only. Randomization will occur at a BL2 phone call. Participants are considered enrolled at BL2 after randomization. Adolescents invited to begin the study intervention within a week after enrollment.

Documentation of Reasons for Ineligibility

All participants who express interest in the study (i.e., make contact with us regarding the study) will be tracked in a separate database along with the status of their participation. Any participant who is screened by phone for any aspect of the study including Phase 2, Phase 3 Study A, and Phase 3 Study B (even if only one inclusion criterion is assessed before the participant is determined not eligible) will have a study record documenting which inclusion criteria were assessed and the outcome of that assessment (i.e., as part of a study log). The study record is linked to the participant's name and other personal identifiers only by the study ID number. Once study

status is determined (i.e., determination that a person is not eligible and the reason), we will not retain the names of potential participants if they have not signed a consent form.

5. STUDY INTERVENTIONS

5.1 Interventions, Administration, and Duration

Yoga classes are administered to a group of participants. Participants attend classes once per week; they will also be asked to practice yoga at home. Classes will take place in a room on the Butler Hospital campus; they are planned to be 45 minutes long. Registered yoga teachers will deliver the intervention. Potential risks include loss of privacy or breach of confidentiality, increased distress due to procedures, ineffective intervention (i.e., lack of improvement in depression symptoms), and mild physical injury.

Group CBT is administered to a group of participants. Participants attend groups once per week; they will also be given homework assignments. Classes will take place in a room on the Butler Hospital campus. Therapists will have a master's degree or Ph.D. in psychology or a related field (e.g., social work). Potential risks include loss of privacy or breach of confidentiality, increased distress due to procedures, and ineffective intervention (i.e., lack of improvement in depression symptoms).

COVID Modifications

In the event we are unable to hold in-person classes (i.e., due to a major public health emergency), we will hold classes via videoconference. This would be through the use of HIPAA-compliant videoconference service.

We will send information about accessing the videoconference to participants via email, according to preferences for method of contact indicated by participants/ parents/guardians during the baseline consent process.

For participants who began study prior to COVID modifications (and therefore had an opportunity to switch to remote participation after consenting to and participating in in-person participation): Prior to sending out video links and holding video-based classes, we will conduct telephone consent / assent for remote participation with parents and teens, and document that they understand risks and benefits of remote participation, and consent/ assent to participate. We will use an IRB-approved script to do this. Any participants who have already consented to receiving REDCap links via email will also be asked if they would like to receive a REDCap link that will bring them to a written version of that oral consent script, so that they may follow along with the consent.

Participants who begin study after COVID modifications will be consented in all processes at the baseline visit. These participants will have study materials (mat and blocks for yoga, or CBT workbook) mailed or dropped off at their house. In addition, these participants will be required to have their cameras on while participating in study interventions.

5.2 Handling of Study Interventions

Yoga Intervention

Yoga classes. The manualized hatha yoga program will begin with a 30-minute initial

individual session with a yoga teacher, to introduce the participant to yoga and give them a chance to privately ask any questions or express any concerns. In this individual session, teachers will focus on how to practice yoga in a way that is physically safer, and review signs that a participant should alter or back out of a pose.

Subsequently, participants will be asked to attend one 45 minute class per week for 12 weeks. Each class will consist of: introduction of a theme; pranayama (breathing practices); standing postures (asanas); floor postures; inversions; guided savasana (relaxation); and home practice assignments. Classes will emphasize breath-linked movement and moderate physical activity. Class size will range between 1 and 12 participants.

Yoga Home Practice. Home practice will be essential for increasing yoga “dosage.” When participants first start class, we will give them a yoga mat to take home. In each class, the yoga instructor will review specific practices and recommend that participants try those practices at home. The practices will always be ones that carry with it minimal risk of injury, and instructors will go over safe practice in class. Sample practices that may be introduced for homework include: 3-part breath, a cat-cow-child sequence, and a half sun salutation. Participants may continue in the study regardless of whether they practice at home.

Yoga Instructors. The Yoga Alliance is a professional organization which sets standards for yoga teacher training. One can be a Registered Yoga Teacher (RYT) at the 200- or 500-hour level. Experienced Registered Yoga Teachers (E-RYT) at the 500-hour level have at least 4 years of experience and 2000 hours teaching, and are qualified to train teachers and provide continuing education. We will require that all study yoga teachers be RYT^s and will have previous experience working with adolescents. Teachers will also have study-specific training on research methods, working with depressed adolescents, and the yoga manual. They will meet approximately monthly for supervision. There will be at least 2 trained yoga teachers. Yoga supervisors will also review audio recordings of classes to assess instructor adherence.

Yoga instructor Manual Fidelity. All classes will be audio recorded. After training, [name] and [name] will rate 10% of all classes for adherence to the yoga manual. Similar to previous research, they will use an adherence scale which consists of a) a checklist of required practices or types of practices as specified in the manual; and b) ratings (satisfactory, unsatisfactory) on core principles as detailed in the manual. If an instructor leads a class that fall below 80% adherence on either scale, it may be grounds for re-training. However, because this is a treatment development study, this may also be an indicator that the manual itself needs to be clarified. [name] will consult with lead yoga instructor [name] on this possibility, and make small clarifications to the manual as needed. Any larger changes deemed necessary would occur after the open trial or pilot RCT (unless they are immediately necessary for participant safety).

Group CBT

Groups. We will adapt the Stress and Your Mood manual and workbook to guide group CBT for depression [16]. This manual focuses on core CBT skills, including behavioral activation, communication and social skills, problem-solving, and cognitive restructuring. They will be given optional assignments to complete at home. Prior to the start of class, participants will have a 30-minute individual meeting with one of the group therapists to orient them to the group. Class size will range between 1 and 12 participants. There will be at least 2 trained therapists for this group.

Homework. Participants will be given optional assignments to complete at home.

Therapists. Therapists will have a master's degree or Ph.D. in psychology or a related field (e.g., social work), and will have previous experience with CBT and with adolescents. The therapist will have study specific-training and will meet approximately monthly for supervision. [name] will review audio recordings to assess therapist adherence to the study manual.

CBT Therapist Manual Fidelity. Procedures will mirror procedures used for yoga teachers. After training, [name] or a qualified co-Investigator will rate 10% of all groups for adherence to the therapist manual. They will use a checklist to assess fidelity to the manual for each class, and a separate scale to assess adherence to core principles of CBT. Any classes that fall below 80% adherence will be grounds for re-training.

5.3 Concomitant Interventions

5.3.1 Allowed Interventions

Once a participant is enrolled in the study, participants will not be excluded for any concomitant intervention. For example, if a participant begins outside yoga classes while they are in the study, we will record that information, but not require that they discontinue study interventions. If a participant changes their dose of antidepressant medication, or outside therapy, we will record that information, but not require that they discontinue study participation.

5.3.2 Required Interventions

None.

5.3.3 Prohibited Interventions

None.

5.4 Adherence Assessment

Yoga Participant Adherence. To be considered adherent, a participant must attend 8/12 classes and engage in home practice at least 2 times per week for 8/12 weeks (as assessed via self-report).

CBT Participant Adherence. Participant adherence is defined as number of groups attended; we define "satisfactory" adherence as attending 8/12 groups.

6. STUDY PROCEDURES

6.1 Schedule of Evaluations

Table 1. Schedule of Evaluations, Phase 1.

| Assessment | Phone Screening: (Day-30 to Day-1) | Baseline, Enrollment, Visit 1 (Day 0) |
|--|---------------------------------------|--|
| Inclusion/Exclusion | X | |
| PHQ-8 | X | |
| Informed Consent Form | | X |
| Demographics and Psychotherapy Practice Scale-Patient Depression Care Version | | X |
| Payment – Adolescent | | \$35 |
| Payment – Parent | | \$35 |

Table 2, Schedule of Evaluations, Phase 2 and Phase 3.

| Assessment | Type of Assessment | Phone Screening: (Up to 30 days before BL1) | Baseline 1, Visit 1 | Baseline 2; must occur with 14 days of BL1 | After initial class | Weekly M1, M2, M3 | M1 visit | M2 visit | M3 visit | M6 visit (Phase 3 only) | M9 visit (Phase 3 only)** |
|--|---------------------------|---|---------------------|--|---------------------|-------------------|----------|----------|----------|-------------------------|---------------------------|
| Inclusion/Exclusion (A) | Interview, pre-randomize. | X | X | | | | | | | | |
| Informed Consent Form (A/P) | Pre-randomize. | | X | | | | | | | | |
| Enrollment – Phase 2 | Interview, non-blind RA | | X | X | | | | | | | |
| Enrollment and Randomization – Phase 3 | Interview, non-blind RA | | | X | | | | | | | |
| CEQ (A) | Self-report, non-blind DB | | | | X | | | | | | |
| CSQ-8 (A/P) | Self-report, non-blind DB | | | | | | | | X | | |
| Qualitative Interview (A/P) | Interview, non-blind RA | | | | | | | | X | | |
| Homework Questionnaire (A) | Self-report, non-blind DB | | | | | X | | | | X | X |
| Injuries due to yoga (A) | Self-report, non-blind DB | | | | | X | | | | | |
| SAFTEE (A/P) | Interview, non-blind RA | | | | | | | | X | | |
| Pregnancy (A) | Interview, non-blind RA | | X | | | | X | X | X | | |
| Other Adverse Events | Interview, non-blind RA | | X | X | | X | X | X | X | X | X |
| QIDS-A-CR (A/P) | Interview, blind RA | | X | | | | X | X | X | X | X |
| BDI (A/P) | Self-report, blind DB | | X | | | | | | X | X | X |
| CIS (A/P) | Self-report, blind DB | | X | | | | | | X | X | X |

| Assessment | Type of Assessment | Phone Screening: (Up to 30 days before BL1) | Baseline 1, Visit 1 | Baseline 2; must occur with 14 days of BL1 | After initial class | Weekly M1, M2, M3 | M1 visit | M2 visit | M3 visit | M6 visit (Phase 3 only) | M9 visit (Phase 3 only)** | |
|---|--------------------------|--|---------------------|--|---------------------|-------------------|----------|----------|----------|-------------------------|---------------------------|------|
| SCARED (A/P) | Self-report, blind DB | | X | | | | | | X | X | X | |
| TMS (A) | Self-report, blind DB | | X | | | | | | X | | | |
| SCS (A) | Self-report, blind DB | | X | | | | | | X | | | |
| Yoga Practice (IPAQ format) (A) | Interview, non-blind RA | | X | | | | | X | X | X | X | |
| TRAQ (A/P) | Interview, blind RA | | X | | | | | | X | X | X | |
| CASA (A/P) | Interview, blind RA | | X | | | | | | X | X | X | |
| Psychotherapy Practice Scale – Pt Depression Care Version (A) | Self-report, blind DB | | X | | | | | | | | | |
| PROMIS Sleep disturbance scale (A) | Self-report, blind DB | | X | | | | | | X | | | |
| Demographics (A/P) | Self-report, blind DB | | X | | | | | | | | | |
| MINI (A/P) | Interview, pre-randomiz. | | X | | | | | | | | | |
| MINI Mania/hypomania and Suicidality Modules (A) | Interview, blind RA | | | | | | | | X | X | X | |
| PHQ-8 (A) | Interview, pre-randomiz. | X | | | | | | | | | | |
| Teen treatment arm preference (A) | Self-report, blind DB | | X | | | | | | | | | |
| Perceived Cohesion Scale (A) | Self-report, blind DB | | | | X | | | | X | | | |
| Payment – Adolescent | | | \$30 | | | | | \$20 | \$20 | \$30 | \$40 | \$50 |

| Assessment | Type of Assessment | Phone Screening: (Up to 30 days before BL1) | Baseline 1, Visit 1 | Baseline 2; must occur with 14 days of BL1 | After initial class | Weekly M1, M2, M3 | M1 visit | M2 visit | M3 visit | M6 visit (Phase 3 only) | M9 visit (Phase 3 only)** |
|------------------|--------------------|--|---------------------|--|---------------------|-------------------|----------|----------|----------|-------------------------|---------------------------|
| Payment – Parent | | | \$30 | | | | \$20 | \$20 | \$30 | \$40 | \$50 |

Abbreviations: time points: M1, M2, M3 = months 1, 2, and 3, respectively; M6*, M9* = follow-up assessments at months 6 and 9, RCT only.

Assessee: A = adolescent; P = parent; A/P = both. RA = research assistant; DB = database.

** M9 visit only included for participants who signed a consent form version dated 12/1/2020 or earlier.

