If participants meet all eligibility criteria and are able to provide proof of medical clearance for physical activity at their BL1 visit, they are considered enrolled at their BL1 visit. BL1 visit date is recorded as the enrollment date. Participants for whom we need to request medical clearance for physical activity will need to have a second Baseline 2 contact (phone call) scheduled once we have obtained the medical clearance. BL2 must occur within 14 days of BL1. They are considered enrolled at BL2.

Enrollment and Randomization – Phase 3

Randomization occurs in Phase 3 only. Allowable window between BL1 and randomization (BL2 timepoint) is 14 days. Participants are considered enrolled at BL2 after randomization. The participant is invited to begin the study intervention within 1 week of randomization.

Payment – Phases 2 and 3

Payment to adolescents for completion of this visit is \$30. Payment to parents for completion of this visit is \$30.

6.2.3 Blinding – Phase 3

Blinding will occur in Phase 3 only. We propose to have one blinded PI and one blinded RA on this project. [name] will be the non-blind PI and will primarily be responsible for supervision of the interventionists and ensuring therapist/yoga instructor adherence. [name] will be the blind PI and will be primarily responsible for the supervision of the assessors (including rating ambiguous data on outcome measures), and monitoring retention of study participants in aggregate, not by study arm. [name], the study statistician, will be blind to group assignment (and will have no contact with participants.) When there is a question about whether a participant meets inclusion criteria, [name] will make a decision about inclusion. [name] and non-blind RA will meet separately to discuss intervention-specific concerns (e.g., need to cancel class due to lack of participants). Co-I [name] will also assist with supervising assessors, and will be blind to treatment group. Project Manager [name] will not be blind.

To ensure that blindness will be maintained, we will have two separate REDCap modules/databases. One will contain study participant data that does not indicate participant randomized assignment; the other will have intervention-specific data (e.g., dates of sessions attended, yoga homework) that only the non-blind PI and RA will have access to.

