In this study, we conduct assessments with both the adolescent and parent, typically at the same time. Both RAs are blind to treatment group at baseline, as it has not yet been assigned. The non-blind RA will conduct the randomization. For follow-up assessments, we have detailed in Table 2 above whether the blind or non-blind RA will conduct a particular assessment.

In reporting adverse events to the Independent Monitoring Committee, determination of “causal relationship” will be made by the non-blind PI only, as it may require knowledge of which intervention arm the participant is in. The standard Adverse Events Reporting Form of our IRB does not ask for intervention arm; thus risk of un-blinding from AE reporting is minimal.

Either PI can conduct suicide or other risk assessments. If the blind PI is conducting a risk assessment, she will remind the participant not to reveal the intervention arm. In the unlikely event that a risk assessment is needed during class and the blind PI needs to conduct the risk assessment, the non-blind RA will bring the participant to a neutral location for assessment.

The non-blind PI will meet with yoga instructors and CBT therapists for supervision. The *Protocol Template, Version 3.2*

instructor/ therapist adherence ratings will be conducted by the non-blind PI and RA.

We will keep a record of any instances of un-blinding. This record will be used to improve procedures for a larger clinical trial. After all data are collected and the database is locked, the blind PI may be un-blinded so as to contribute to data interpretation.

Participants and parents cannot be blind to study intervention. However, we will present both interventions (CBT or yoga) with equipoise to all participants in written materials and orally.

6.2.4 Follow-up Visits – Phases 2 and 3

For the purposes of targeting dates for an assessment, we will consider each month = 28 days (4 weeks exactly). For all follow-up assessments, research staff will make every effort to conduct the assessment within one week before or one week after the exact due date of the assessment. However, because all data can be analyzed with modern statistical methods regardless of whether it was collected inside that window, RAs will still collect data if possible even if it is later than that two-week window. We will record optimum date for the assessment (e.g., Enrollment + 84 days for M3 assessment) as well as the actual date of the assessment.

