7.1 Specification of Safety Parameters

Safety issues will be minimal in Phase 1 given that participation involves only a single focus group, no yoga classes, and no formal assessment of suicidality. However, should an issue arise (e.g., a voluntary report of suicide ideation from one of the adolescent participants), staff would manage it in the same way that they would manage it in Phases 2 and 3.

Please see Table 3 for a summary of safety issues, how they are assessed, when they are assessed, and relevant staff actions.

Table 3. Assessment and Management of Safety Issues, Summary, Phases 2 and 3.

| Safety Issue | How assessed | When Assessed in Phase 2/Phase 3 | Relevant Research Staff Actions |
|------------------------|--|---|---|
| Suicidality | QIDS, BDI, MINI Participant/parent report to research staff | B1, M1, M2, M3, M6*, M9* B1, M3, M6*, M9* Any point | Immediate clinical assessment as described in DSMP |
| Clinical deterioration | Change in QIDS score | M1, M2, M3, M6*, M9* | Immediate clinical assessment as described in DSMP |
| Injuries due to yoga | Structured self-report | Weekly during first 3 months | Follow until resolution; may result in changes to yoga instructor manual |
| Pregnancy | Single interview question | BL1 (exclusion) M1, M2 | Discontinuation from intervention |
| Other AEs | SAFTEE CASA Participant/parent report to research staff | M3 BL1, M3, M6*, M9* Any point | If related to study participation, follow resolution; potential changes to procedures particularly if AE is also unexpected |

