curiosity subscale [27]. We will assess self-compassion with the 26-item Self-Compassion Scale (SCS)[28]. This scale can yield a general self-compassion score and has previously been used with adolescents [29].

Other assessments. Finally, we will use the International Physical Activity Questionnaire (IPAQ) [30], a self-report measure of physical activity. We have also adapted this scale to measure amount of yoga practice participants engaged in during the follow-up time period. We will assess antidepressant medication use with the interview-based Treatment Response to Antidepressant Questionnaire (TRAQ) [31]). We will use the Child and Adolescent Services Assessment (CASA)[32] interview to assess other mental health treatment. If a participant is engaged in psychotherapy but the participant and parent are unclear as to whether it is CBT, we will use the Psychotherapy Practice Scale-Patient Depression Care Version [33] to help determine whether it is likely that the participant is engaged in CBT. This questionnaire will be modified to include some open-ended questions about the nature of the participant's psychotherapy. We will use the Perceived Cohesion scale to assess group cohesion.

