10. DATA COLLECTION AND QUALITY ASSURANCE

10.1 Data Collection Forms

Participants will directly enter self-report data into REDCap, and data collected as part of an interview will be written on a paper CRF and double-entered into REDCap. For the RCT (Phase 3), there will be two REDCap databases – a “blind” database and a “nonblind” database. As described in the assessment table, some assessments are described as being collected by a blind evaluator (research assistant), whereas some are not (because these assessments, by their nature, would break the blind.) There will also be a database that we will use for tracking participants.

Any data, forms, reports, audiorecordings, and other records that leave the site will be identified only by a participant identification number (Study ID, SID) to maintain confidentiality. All paper records will be kept in a locked file cabinet. All data collected will be entered into an electronic database which is stored on a secure server (REDCap) that is backed up on a daily basis. Participant identifying information will be stored in a separate database and will be password protected and stored on a secure server. Care New England’s instance of REDCap has been deemed HIPAA compliant by CNE Information Technology.

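### The one blind RA gives both the QIDS and the post-baseline CASA services interview, which risks accidentally revealing the arm to the depression rater

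*Combined protocol and SAP*

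**What the plan says.** Table 2 in section 6.1 gives the depression interview to the blind assessor ("QIDS-A-CR (A/P) | Interview, blind RA") at BL1, M1, M2, M3, M6 and M9. It gives the services interview to the same role ("CASA (A/P) | Interview, blind RA") at BL1, M3, M6 and M9. Both are done with the adolescent and the parent. A footnote limits M9 to participants whose consent form version is dated 12/1/2020 or earlier.

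Section 6.2.3 sets the staffing: "We propose to have one blinded PI and one blinded RA on this project". It also makes Table 2 binding: "For follow-up assessments, we have detailed in Table 2 above whether the blind or non-blind RA will conduct a particular assessment".

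Section 9.1.2 first covers antidepressant use with the TRAQ and then states the purpose of the CASA: "We will use the Child and Adolescent Services Assessment (CASA)[32] interview to assess other mental health treatment".

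Section 10.1 explains why some assessments are not collected by the blind evaluator: "because these assessments, by their nature, would break the blind". Section 3 limits the blind evaluator to outcomes that do not refer directly to the study arm.

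**The concern.** Group CBT is itself a mental health treatment, delivered by therapists with a master's degree or Ph.D. (sections 5.1 and 5.2). A teen or parent asked at the end of treatment about mental health services may mention the weekly group, and the person asking is the person who rates the QIDS.

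The blind rating is the plan's safeguard for that score. Sections 1.1 and 9.5.2 make the adolescent QIDS at M3, rated blind, the main depression measure here and the intended primary outcome of the later efficacy trial. Baseline is rated before randomisation. Any shift in scoring after the rater learns the arm would therefore go straight into the baseline-to-follow-up change, which is what the within-arm tests and effect sizes use. The pilot also exists to settle procedures for the next trial, so a weak point in the assessor assignment would be carried forward.

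**Working it through.** No formula in the plan bears on this. The check sets the schedule, the staffing and the safeguards side by side.

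**1. Same person.** Table 2 assigns both interviews to the blind RA. Section 6.2.3 has one blind RA and says Table 2 decides who does each follow-up assessment. The QIDS rater is therefore also the CASA interviewer.

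**2. Which QIDS ratings are exposed (Table 2).**

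| Visit | QIDS by blind RA | CASA by blind RA | QIDS exposed through the CASA? |
|---|---|---|---|
| BL1 | yes | yes | No: before randomisation |
| M1, M2 | yes | no | No: no post-baseline CASA yet |
| M3 | yes | yes | Only if a teen or parent CASA precedes the rating |
| M6 | yes | yes | Yes, in any order: the M3 CASA is already done |
| M9 (older consents) | yes | yes | Yes, in any order, as at M6 |

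The M3 visit list in section 6.2.4 names the QIDS before the CASA but is not stated to be an order of administration. Section 6.2.3 adds that teen and parent are usually assessed at the same time, so a parent CASA could come before a teen QIDS.

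**3. How the plan treats similar interviews.** Table 2 sends the Yoga Practice interview, the SAFTEE and the qualitative interview to the non-blind RA. Yoga Practice is the closest parallel, since it asks about exposure to one arm's type of treatment. The CASA can touch the other arm's type of treatment but stays with the blind RA.

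**4. Safeguards.** The only stated reminder not to reveal the arm (section 6.2.3) covers risk assessments done by the blind PI. No passage has the blind RA ask families to leave out study classes during the CASA, fixes a QIDS-first order, or replaces a rater after disclosure. Instances of un-blinding are recorded.

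**5. Size.** The shift in an arm's mean QIDS would be (share of ratings made after disclosure) × (average change in score once the rater knows the arm). The documents give neither factor, nor the direction of the second, so no figure follows.

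The number of CBT families who could disclose can be bounded. Assuming an even split, Study A has 34 / 2 = 17 CBT teens and Study B at most 20 / 2 = 10, so at most about 17 + 10 = 27 teens, plus those parents who take part.

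**The case against.** The strongest reply rests on one word. Section 9.1.2 says the CASA is an "interview to assess other mental health treatment". Coming after antidepressant use, this reads naturally as services outside the study, and on that reading a correct answer leaves out the study group. A reader might infer that any honest CASA answer names the arm. The documents do not support that: the items are not reproduced, and the stated purpose points the other way. What remains is accidental disclosure by families who have not been told of the distinction.

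There is also a reason to keep the CASA blind. Co-interventions recorded by someone who knows the arm may be recorded differently by arm. That stands as a real trade-off.

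The consequence is limited too. Table 4 makes feasibility, acceptability and safety primary and labels depression change exploratory. Section 9.6 tests it within arm, and section 9.1 says the study is not powered for differences or non-inferiority. The BDI, CIS and SCARED are self-report. The un-blinding log is meant to improve procedures for a larger trial, which is a fair use of a pilot, although it acts only after the event. Section 10.3.3 has 10% of QIDS interviews re-rated. That checks agreement between raters, and it leaves most ratings unchecked.

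Table 3 (section 7.1) lists the CASA as a source of other adverse events ("SAFTEE CASA Participant/parent report to research staff"), while Table 2 gives adverse events to the non-blind RA. A reader might take this as further evidence of un-blinding. It is only a mismatch: section 7.3 does not count the CASA among its three ascertainment methods, and in Phase 3 only the non-blind PI codes events (section 7.4).

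**Conclusion.** The point holds as an avoidable risk to the blind. The schedule puts a services interview that could draw out study CBT in the hands of the only blind QIDS rater, with no script and no fixed order. The risk is conditional for the M3 QIDS and independent of order for M6 and, under the older consents, M9. M1 and M2 are not affected by this route.

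It rests on two assumptions: that some teens or parents would mention the study group when asked about services, and that knowing the arm could influence a clinician-rated score. The documents settle neither, so the size stays open.

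Two stronger conclusions should not be drawn. One is that the depression results are invalid. They are exploratory within-arm estimates, and the primary feasibility and acceptability aims are untouched. The other is that the possible bias can be judged against the 2-point limit in section 10.3.3. That limit concerns disagreement on the total score of a single interview and says nothing about a shift in an arm mean.

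The change is worth making because it is cheap and because the QIDS procedure is intended for the next trial.

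**What to change.** In Table 2, keep the baseline CASA as it is. Change the CASA at M3, M6 and M9 to an interview by the non-blind RA, with the form in the non-blind REDCap database. This removes the route at every visit, including carry-over. State in section 9.1.2 whether the CASA covers study classes, and bring the adverse-event entry in Table 3 into line with Table 2 and section 7.3.

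The cost is one table row, one form moved and some interview time shifted between existing staff. The non-blind RA already interviews adolescents at M3, M6 and M9 (Yoga Practice) and parents at M3 (SAFTEE, qualitative interview). Table 2 shows no non-blind interview marked for parents at M6 or M9, so a parent interview may have to be added there. Co-interventions would also be collected by someone who knows the arm.

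If the sponsor prefers blind collection of co-interventions, the alternative is to complete and lock both the adolescent and the parent QIDS before any CASA at each visit, and to add a scripted request not to mention study classes. This protects the M3 rating from a CASA at the same visit but leaves some carry-over risk at M6 and M9.
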